#### Sample size calculation

There were not enough previous studies available to determine the sample size needed to evaluate the effectiveness of the Utstein CPR program bundle. Prior to the initiation of the study, the sample size was estimated assuming a survival rate of 9% during the control period and an 11% survival rate during the experimental period. For each group of patients, 4,035 were needed to assess significant differences based on 80% of power and 0.05 of alpha.

#### Statistical analysis

The demographic findings and survival outcomes of the study population by study period are compared. The continuous variables were compared using the Wilcoxon rank sum test and the categorical variables were compared using the chi-squared test. The temporal trends by study period with six-month interval on performance indicators for each intervention were evaluated by the Cochran-Armitage test for the trends. We calculated the absolute differences (AD) with 95% confidence intervals (CIs) of the outcomes between the study periods and between the patient groups receiving each CPR program. A mixed-effects logistic regression model using the GLIMMIX procedure was used to estimate the association between the study period with outcomes, adjusting for the following: demographics (Model 1); demographics, community factors, and EMS factors (Model 2); demographics, community factors and EMS factors, and post-resuscitation care factors (Model 3); and finally, demographics, community factors and EMS factors, ACLS factors, and post-resuscitation care factors (Model 4). Outcomes were compared to assess the overall effect of all programs administered to patients before and after intervention. To assess the

individual effects of each program, a multi-variable logistic regression analysis was performed to evaluate the association between individual programs and outcomes. We constructed a mixed-effects logistic regression model to test the association between each CPR program (DACPR, MTR, and FCPR) and outcomes that was adjusted for potential confounders. We included random intercepts for ambulance station to control for clustering within the ambulance stations in both models. The effect sizes were calculated with AOR and 95% CIs. The p value was set at 0.05, and all statistical tests were 2-tailed. All statistical analyses were performed using the SAS version 9.4 software (SAS Institute Inc., Cary, NC, USA) and R version 3.4.1 (available at <https://www.rproject.org>. accessed on Feb. 25, 2018).

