**NCTo2540629**

**08/06/2015**

## Study protocol

### Study design and Setting

This study was a before and after study of the implementation of a bundle of UTIS CPR programs in Seoul Metropolitan City. The before phase was defined as January 2013 through December 2014 and included a historic control population. The after phase was defined as January 2015 through December 2016.

Seoul has approximately 10 million inhabitants per 605 km^2. The SMFD provides fire-based and public service under 24 EMS agencies with 140 ambulances with a single unified dispatch center, with approximately 300,000 transports per year including 4,800 OHCAAs. EMS providers can provide care comparable to an intermediate emergency medical technician (EMT-I) level in the United States. EMTs cannot declare death or stop CPR in the field unless a return of spontaneous circulation (ROSC) occurs. Therefore, all patients with OHCA are transported to emergency departments (EDs) while receiving CPR in an ambulance. The EMS CPR protocols were revised on the 2010 and 2015 International guidelines.

In Seoul, a DACPR program was implemented in 2010 and has been in effect for all calls suspected to involve cardiac arrest. The dispatch center has a standard protocol for DACPR with two steps; 1) screening potential OHCAAs by primary call dispatcher (PCD) and 2) providing telephone CPR instruction by medical call dispatcher (MCD). Prior to 2015, Seoul was covered by a single-tiered EMS service to respond to OHCA events. A nearest and available ambulance was dispatched to an OHCA event. Of the 140 ambulances, only 27 (23.3%) were equipped with a defibrillator with a feedback function until December 2014. However, there was no active feedback CPR training as a feedback to EMTs after review of the CPR records by medical directors.

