### Intervention

A bundle of three UTIS CPR programs were implemented in Jan. 2015; 1) a high-quality DACPR program, 2) a rapid dispatch program using MTR, and 3) an FCPR program using defibrillators with feedback functions. A high-quality DACPR program was implemented in 2015 in addition routine DACPR program. This program included monthly monitoring and evaluation of the quality of the call

receiving and consulting stages by a medical director. Ten percent of the calls correctly identified as cardiac arrest and 10% of the calls not recognized as cardiac arrest were randomly selected based on the records from the ambulance run sheet. The audit reviews were performed in a standardized manner and recorded on an audio review evaluation sheet. Performance standard indicators were set, and feedback for the executive members, including the dispatch center officers and medical directors during the study period. Key performance standard indicators included OHCA detection rate by the PCD and proportion of calls given CPR instructions within 120 seconds. Monthly education conferences for dispatchers were conducted to get feedback of the performance standards per individual and per dispatch teams. The rapid CPR program included a multi-tier response (MTR) using the nearest available fire engine or basic life support vehicle team in addition to routine ambulance dispatch. An MTR scene protocol was developed, and a train-the-trainer model was used to disseminate the protocol. Six education programs were conducted, and 141 (10.8% of all the EMS providers in Seoul) participants from 24 EMS agencies were trained as trainers in 2015. They conducted MTR CPR training programs for all the EMTs and firefighters in Seoul. The FCPR program included the distribution of defibrillators with feedback functions to each ambulance and EMT training program; EMS personnel were also strongly encouraged to use a defibrillator with a feedback function for professional recording of EMS-CPR, and the medical director provided feedback to the individual teams using these defibrillators. All CPR processes were recorded by these devices and uploaded by the EMTs after CPR to an electronic server of the SMFD to be reviewed by the EMS medical directors. The MTR was a newly implemented program, but the other two programs were incomplete before 2015. It is a new attempt in this study to try to apply both programs (DACP and FCPR) robustly and systematically to the whole city EMS.

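### The half-yearly trend test on the performance indicators shows change over time, not change at January 2015; this matters for the DACPR and FCPR indicators

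*Combined protocol and SAP*

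**What the plan says.** The design is a before-after comparison in one city with no concurrent control: "The before phase was defined as January 2013 through December 2014 and included a historic control population" and "The after phase was defined as January 2015 through December 2016" (Study design and Setting). The change point is fixed in advance: "A bundle of three UTIS CPR programs were implemented in Jan. 2015" (Intervention).

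For the process measures, the Statistical analysis section states: "The temporal trends by study period with six-month interval on performance indicators for each intervention were evaluated by the Cochran-Armitage test for the trends". It names no level change, slope change or calendar-time term for these indicators.

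Two of the three programs existed in some form before 2015. On dispatcher assistance, "a DACPR program was implemented in 2010 and has been in effect for all calls suspected to involve cardiac arrest". On feedback devices, "only 27 (23.3%) were equipped with a defibrillator with a feedback function until December 2014" (27 of 140 is 19.3%, so the printed percentage needs checking, but nothing here depends on it). The Intervention section sums this up: "The MTR was a newly implemented program, but the other two programs were incomplete before 2015".

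**The concern.** The Cochran-Armitage test is valid for proportions, and it answers the question of whether an indicator trended. It does not ask when the change happened. In a study with a historical comparison, the useful question about delivery is whether an indicator departed from its previous course once the bundle started.

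For DACPR and FCPR, improvement already under way in 2013-2014 is a live alternative, because both had activity to improve on. A steady rise unrelated to the bundle could then produce a small p-value, and a reader could take it as evidence that the bundle was delivered. At stake is what the study can say about program delivery. The estimated effect on neurologic recovery is not at stake.

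**Working it through.** **Inputs from the documents.** Four half-years before and four after January 2015 (Study design and Setting); two-sided 0.05 (Statistical analysis). The plan gives no expected value, size or power for any indicator, so there is no figure of its own for this test to reproduce.

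**Scale (assumption).** The only sample figure is 4,035 per period (Sample size calculation). Its stated inputs give (1.960 + 0.842)² × (0.09×0.91 + 0.11×0.89) / 0.02² = 3,528, or 3,531 with pooled variance and 3,631 with continuity correction, so 4,035 is not reproduced. It would follow as 3,631/0.90 with a 10% loss that the plan does not state. I use it for scale only: 4,035/4 ≈ 1,009 per half-year. It is not a count of patients or calls.

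**Other assumptions, not in the documents.** Indicator at 50% at the start, equal half-years, no clustering by station.

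**Trend statistic.** With scores t = 1 to 8, Σ(t − 4.5)² = 42, and the expected statistic is about

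Z = Σ(t − 4.5)p_t × √(n/42) / √[p̄(1 − p̄)], with √(1,009/42) = 4.901.

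The chance of rejection is about Φ(Z − 1.96). For the 7-point drift (1 point per half-year): Σ = 42 × 0.01 = 0.42 and p̄ = 0.535, so Z = 0.42 × 4.901/0.4988 = 4.13 and Φ(2.17) = 98.5%.

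The segmented comparator is a logistic model with linear time, a level change and a slope change at January 2015, tested jointly on 2 df by simulation.

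| True pattern | Σ | p̄ | Z | Trend test rejects (formula) | Segmented test rejects (simulated) |
|---|---|---|---|---|---|
| Drift 50% to 57%, nothing at 2015 | 0.420 | 0.535 | 4.13 | 98% | about 5% |
| Drift 50% to 53.5%, nothing at 2015 | 0.210 | 0.518 | 2.06 | 54% | about 5% |
| +2 points per half-year, stopping after 2014 | 0.340 | 0.545 | 3.35 | 92% | 44% |
| Immediate 6-point step at 2015 | 0.480 | 0.530 | 4.71 | 99.7% | about 65% |
| 6 points phased over 2015 (3, 6, 6, 6) | 0.465 | 0.526 | 4.57 | 99.5% | about 32% |
| 6 points phased over 2015-16 (1.5, 3, 4.5, 6) | 0.375 | 0.519 | 3.68 | 96% | about 25% |

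Simulation of the trend test agrees with the formula to within about a point. If 3,531/4 ≈ 883 is used in place of 1,009, the first row becomes Z = 4.13 × √(883/1,009) = 3.86 and 97%.

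**Why the patterns look alike.** The linear scores and the January 2015 indicator correlate at 8/√(42 × 2) = 0.87. A drift of d points per half-year gives the same expected numerator as a step of 42d/8 = 5.25d, so 1 point per half-year resembles a step of about 5 points.

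**The third row** is the plainest case: improvement that ends just as the programs begin is still significant in 92% of trend tests. The segmented test also rejects there in 44% of runs, because the slope does change, but downward. The two changes must therefore be reported with their signs and intervals, not as a joint p-value alone.

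**The other reading of the sentence.** It could mean a separate trend test within each period of four half-years. That would reveal an earlier drift in 82-85% of runs at 2 points per half-year, but in only 29-33% at 1 point. A pure step at January 2015 would be flagged in about 5% of runs in each period, the false-positive rate. Neither reading tests a change at January 2015.

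**The case against.** **The plan does not claim this is a test of implementation.** This stands. A reader might infer that the trend test is offered as the proof that the programs worked, or that it underpins a causal claim. The text says only that trends were evaluated, so the point is about what a significant result can support. Chi-squared comparisons by period might also cover some indicators, but they cannot separate drift from step either.

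**The three programs are not equally exposed.** This also stands. Study design and Setting describes a single-tiered service before 2015, so earlier drift is not a credible account of MTR use. For FCPR, devices were distributed to each ambulance as part of the program, so a rise in use largely reflects roll-out. The concern is strongest for DACPR. The documents give no pre-2015 trend for any indicator, so drift is possible, not shown.

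**A segmented model has its own costs.** Delivery was phased: trainers were trained during 2015 and then taught the rest. Under phasing, power falls to the 25-32% in the table, where the trend test keeps 95% or more. If MTR was zero before 2015 (an assumption), its pre-2015 slope and level change cannot be estimated: a trial fit with four zero half-years gave a step log-odds of 27 with a standard error of about 37,000. Replacing the trend test for every indicator would therefore be unsound. Adding a model for two programs is not.

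**Little is at stake.** This is partly right. The primary result comes from the mixed model on study period, which the trend test does not enter.

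**Conclusion.** The point holds in a limited form. The only time-trend analysis of the performance indicators cannot distinguish a change at January 2015 from a drift already under way, under either reading of the sentence. For DACPR and FCPR, a significant trend is therefore not by itself evidence that the bundle changed performance.

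The absence of a January 2015 term is a fact of the text. The size (98% against about 5% for a 7-point drift) is an illustration that rests on the assumed 1,009 per half-year, 50% start and no clustering; clustering by station would alter both figures.

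The documents do not support going further. They do not show that drift occurred, that the test is invalid, that MTR uptake is in doubt, or that the primary outcome analysis is affected. The point is a worthwhile refinement, not a serious defect.

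**What to change.** 1. Keep the half-year percentages and the trend test as descriptive for all three programs. State whether the test spans all eight half-years or is done within each period, and that its p-value alone is not evidence of a change at January 2015.
2. For the DACPR and FCPR indicators, add a patient-level logistic model with linear calendar time (preferably monthly, which also allows for season), a level change at January 2015, a post-2015 slope change and a random intercept for ambulance station. Report both changes with 95% CIs.
3. For MTR, show the series only.
4. State in advance that power is low (about 65% for an immediate 6-point step and about 25-32% if phased, before any allowance for clustering), so a non-significant result is not failed implementation. State also that a change at January 2015 fixes the timing but does not exclude other changes near that date, such as the protocol revision following the 2015 guidelines.

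The cost is a few sentences of SAP text and one short analysis. Event dates are among the collected variables, and station is already the clustering unit in the outcome models, so no new data are needed. The half-year table alone is not enough, because it carries no station information.

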#### Variables and measurement

Bystander CPR was categorized into the following 3 groups: bystander CPR with dispatcher assistance group, bystander CPR without dispatcher assistance group, and no bystander CPR group. The MTR was positive if more than 2 vehicles arrived to cases with the same accident number. There were two types of MTR including an ambulance-tiered response (ATR) and a fire-engine-tiered response (FTR). FCPR was considered as positive if the corresponding ambulance used a defibrillator with feedback function. We collected following variables 1) demographics (age, gender, past medical history (diabetes mellitus, hypertension, heart disease, and stroke), event date and time (season, weekend, daytime)), 2)

community factors (location of arrest (public vs. private vs. other), witness status, primary cardiac rhythm at the scene (shockable, PEA and asystole), and bystander CPR or defibrillation), 3) EMS factors (EMS defibrillation, prehospital advanced airway, fluid resuscitation, mechanical CPR device use, detection time interval from call to detection of OHCA by the dispatcher, and EMS time intervals (response time interval, scene time interval, and transport time interval), and 4) post-resuscitative care (cardiac reperfusion therapy, targeted temperature management, and extracorporeal membrane oxygenation (ECMO)).

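### The bundle effect comes from an uncontrolled before-after contrast with no secular time term and no outcome trend, so unexplained outcome drift is counted in it

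*Combined protocol and SAP*

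**What the plan says.** Under Study design and Setting, "The before phase was defined as January 2013 through December 2014 and included a historic control population"; the after phase is January 2015 to December 2016. The Intervention section starts all three programs in January 2015. For the whole city, then, study period and bundle are the same variable.

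Under Statistical analysis, mixed-effects logistic models "estimate the association between the study period with outcomes, adjusting for the following: demographics (Model 1); demographics, community factors, and EMS factors (Model 2". Models 3 and 4 add post-resuscitation and ACLS factors, and there is a random intercept for ambulance station. The purpose is stated as follows: "Outcomes were compared to assess the overall effect of all programs administered to patients before and after intervention". A second set of models tests the "association between each CPR program (DACPR, MTR, and FCPR) and outcomes that was adjusted for potential confounders"; neither the confounders nor the years analysed are given.

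The only time variables listed under Variables and measurement are "event date and time (season, weekend, daytime". The only trend analysis is that "temporal trends by study period with six-month interval on performance indicators for each intervention were evaluated by the Cochran-Armitage test".

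Two statements about background matter here. "Prior to 2015, Seoul was covered by a single-tiered EMS service to respond to OHCA events", and the Intervention section describes MTR as newly implemented. The EMS CPR protocols were also revised on the 2010 and 2015 international guidelines; no local adoption date is given.

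**The concern.** Season, weekend and daytime are cyclic. They cannot represent change from one year to the next, and a station intercept cannot either. Whatever moved outcomes between 2013-14 and 2015-16 and is not captured by the covariates therefore goes into the period coefficient. An improvement already under way would be credited to the bundle; a decline would hide part of a real effect. The plan already cuts time into half-years for process measures but not for outcomes, so the reader gets no series by which to judge this.

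The per-program models may share the problem for MTR. If they pool 2013-16 with no period or time term, nearly all before-phase patients sit in the MTR-negative group, and the MTR comparison is partly a comparison of early with late years.

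**Working it through.** **The plan's own figure.** Sample size calculation gives 4,035 per group for 9% vs 11% survival, 80% power, alpha 0.05. The two-sided normal-approximation formula gives 3,531, or 3,631 with continuity correction. Then 3,631/0.90 = 4,034.4, which rounds up to 4,035, but the documents state no 10% allowance. If all 4,035 are analysed, the uncorrected test has 85% power, which is why 85% rather than 80% is the comparator below. The point does not depend on this figure.

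**Inputs.** 9% survival and 4,035 per period (Sample size calculation); two-sided 0.05 (Statistical analysis). The phase midpoints are the starts of 2014 and 2016, 2.0 years apart. Every drift *d* is an assumption and means residual drift after covariates. Accrual is taken as even; clustering is ignored.

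**Two-period contrast.** The spurious difference is 2*d*. The rejection probability is about Φ[(δ − 1.96·SE)/SE], with SE = √(2·p̄(1−p̄)/n). For *d* = 0.5 points/year: δ = 0.010, p̄ = 0.095, SE = √(2 × 0.095 × 0.905/4,035) = 0.00653, and (0.0100 − 0.0128)/0.00653 = −0.43, giving 33%.

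| Assumed drift (points/year), no effect | Spurious difference | OR | p<0.05 |
|---|---|---|---|
| 0.1 | 0.2 points | 1.02 | 6% |
| 0.25 | 0.5 points | 1.06 | 12% |
| 0.5 | 1.0 point | 1.12 | 33% |
| 1.0 | 2.0 points | 1.25 | 85% |

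In the other direction, a true 2-point effect with drift of −0.25 or −0.5 leaves a net 1.5 or 1.0 points, and power falls from 85% to 62% or 33%. The primary outcome (CPC 1 or 2) has no planning rate; at an assumed 4%, 6% or 8%, drift of 0.5 gives 58%, 45% or 36%.

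**What the 2013-14 slope can show.** SE = √(p(1−p)/(N·var(t))), with var(t) = 0.333 years² for 24 equal months. At 9% and N = 4,035, SE = √(0.0819/(4,035 × 0.333)) = 0.0078, so the 95% CI is ±1.5 points/year. Drift of 0.5 or 1.0 would be significant 10% or 25% of the time. Study design and Setting gives "approximately 300,000 transports per year including 4,800 OHCAAs". Even 2 × 4,800 = 9,600, before exclusions, gives ±1.0.

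**What a segmented model costs.** Over 48 months the level change has about 4.0 times the variance of the two-period contrast. At a 10% rate the SE goes from 0.67 to 1.34 points, power for 9% vs 11% from 85% to 32%, and the difference detectable with 80% power from 1.9 to 3.7 points. In 3,000 simulated data sets without covariates or clustering, no effect and drift of 0.5 or 1.0, the two-period test rejected in 34% or 85% and the level-change test in about 5%.

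**MTR, if all years are pooled.** Assume no before-phase MTR, a constant share *s* of after-phase patients receiving it, no MTR effect and drift of 0.5. The period means are 9% and 10%, so the MTR-negative mean is [9 + 10(1−*s*)]/(2−*s*) and the spurious difference is 1/(2−*s*) points. For *s* = 25%, 50% or 75% this is 0.57, 0.67 or 0.80 points, with p<0.05 in 9%, 15% or 22%. With a period term, simulation returns about 5%.

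That last result needs a constant share. If the share rises linearly to 75% over one year and then holds, a period term alone leaves about 0.25 points (6% rejection).

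**The case against.** The design is declared openly as before-after with a historic control, and the model sentence already speaks of association. The covariates may absorb part of any drift. No figure in the documents supports any residual drift, and the top case assumed here equals the whole planned effect. The segmented model can settle little at 32% power. A concurrent control is not available for a city-wide rollout.

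Much of this stands. It is why the two-period contrast should stay, why the segmented model is supportive only, and why no bias is claimed. It does not remove the gap. The text also reads the contrast as the overall effect of the programs and offers no outcome trend. Heavier adjustment is no remedy, because the factors added from Model 2 on include bystander CPR, detection interval and response interval, which the bundle itself targets.

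Two stronger readings are tempting. One is that before-phase patients are MTR-negative by design, so the MTR estimate is certainly confounded. The documents do not go that far: MTR is classified by the vehicles reaching an incident, not by phase; no before-phase count is given; and neither the years analysed nor the confounders are listed. The other is that a period term, a calendar-time term and restriction to 2015-16 are interchangeable remedies. They are not if uptake rose during the after phase, which the trainer program run in 2015 makes plausible.

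**Conclusion.** The omission is confirmed for the period models: no concurrent control, no secular time term, no outcome trend, and a contrast read as the effect of the programs. Residual drift would be counted in that effect. Its size and direction are unknown; the percentages show sensitivity under assumed linear drift, not an estimate of actual bias, and most concern survival, the secondary outcome. A reader might infer that the bundle result is biased; the documents give no yearly rates from which to say so.

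For MTR the point is conditional: it holds if 2013-16 is pooled without a time term. The plan should be amended on both counts, since the remedy is cheap.

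**What to change.** Keep the two-period contrast.

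1. Report the primary outcome and survival for all eight half-years, with the 2013-14 slope and its 95% CI. State that the slope can reveal only large drift.
2. Add a segmented model (calendar time, level change, slope change) as a supportive sensitivity analysis, labelled post hoc if set after outcomes are seen. Use the Model 1 covariates plus witness status, arrest location and, if judged unaffected by the bundle, initial rhythm. Leave out bystander CPR, detection interval and response interval. Cost: about four times the variance for the level change, so a null result is not evidence of no effect.
3. State the analysis set and covariates of the per-program models, and include calendar time, together with study period if 2013-16 is pooled. A period indicator alone, or restriction to 2015-16, is enough only if uptake was stable within the after phase. Cost: MTR is then estimated from after-phase patients. With a period term, power for 9% vs 11% is 47%, 56% or 43% instead of 53%, 75% or 83% at a constant MTR share of 25%, 50% or 75%.
4. State when the 2015 guideline revision was adopted locally. If that falls in the after phase, name it as a co-intervention that cannot be separated from the bundle.
5. Replace the wording about overall and individual effects with before-after association, whatever the segmented model shows.

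Event date is already collected, so the work is analysis text and a few model terms. Only the guideline adoption date is new.

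### Models 3 and 4, as written, adjust prehospital ROSC for hospital care that follows it; Models 2–4 also appear to adjust the period comparison for steps the bundle is meant to change

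*Combined protocol and SAP*

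**What the plan says.** The Statistical analysis section describes a mixed-effects logistic model "used to estimate the association between the study period with outcomes, adjusting for the following: demographics (Model 1"), followed by "demographics, community factors, and EMS factors (Model 2); demographics, community factors and EMS factors, and post-resuscitation care factors (Model 3") and then "demographics, community factors and EMS factors, ACLS factors, and post-resuscitation care factors (Model 4"). No model is restricted to particular outcomes. The Main outcomes section lists three: CPC 1 or 2 at discharge (primary), survival to discharge (secondary) and prehospital ROSC (tertiary).

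The purpose of the period comparison is stated as: "Outcomes were compared to assess the overall effect of all programs administered to patients before and after intervention". Unadjusted results are also planned: "We calculated the absolute differences (AD) with 95% confidence intervals (CIs) of the outcomes between the study periods". The plan does not say which of the four models answers the stated purpose.

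Covariates are named by group in the Statistical analysis section and by item only in Variables and measurement. There, the last group is "post-resuscitative care (cardiac reperfusion therapy, targeted temperature management, and extracorporeal membrane oxygenation (ECMO"). Community factors include location of arrest, witness status, rhythm, and bystander CPR or defibrillation. The bystander CPR variable has a dispatcher-assisted level: "Bystander CPR was categorized into the following 3 groups: bystander CPR with dispatcher assistance group". EMS factors include the "detection time interval from call to detection of OHCA by the dispatcher, and EMS time intervals (response time interval" and others).

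**The concern.** There are two separate problems.

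**Care after the outcome.** Prehospital ROSC is settled before the patient receives reperfusion, temperature management or ECMO. A variable that follows the outcome cannot confound it. Whether a patient receives such care depends heavily on whether ROSC occurred, so conditioning on it can move the period odds ratio for reasons unrelated to the bundle, such as a change in hospital practice between 2013–2014 and 2015–2016.

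**Steps on the causal path.** The Intervention section describes a dispatcher program judged on detection of arrest and prompt CPR instruction, and a rapid-dispatch program that sends an additional vehicle. Bystander CPR, the call-to-detection interval and the response interval are steps through which these programs could work. A model that holds them fixed leaves out the effect they carry. Its period odds ratio would answer a different question from the stated one, while looking like the better-controlled estimate because it contains more covariates.

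**Working it through.** The documents give no rates for ROSC, later care or bystander CPR, so the plan has no figure on this point to reproduce. The only relevant figures are the 9% and 11% survival rates in Sample size calculation, which imply an odds ratio of (0.11/0.89)/(0.09/0.91) = 1.25. I use these as a convenient scale. All other inputs are assumptions. Station clustering and other covariates are ignored.

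**1. ROSC and later care.** Let R be prehospital ROSC and C one binary later-care variable. By Bayes' rule, within stratum C = c:

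period OR in stratum = true OR × [P(c|R=1, after)/P(c|R=0, after)] ÷ [P(c|R=1, before)/P(c|R=0, before)]

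If use of care given ROSC status is the same in both periods, the multiplier is 1 and nothing is lost. If it changes, the multiplier generally departs from 1, although offsetting changes could cancel.

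Assume P(C=1|R=0) = 0.02 in both periods, ROSC 9% before and 11% after. For use among ROSC patients rising from 20% to 30%:
- stratum C = 0: 0.70/0.80 = 0.875, so 1.25 × 0.875 = 1.09
- stratum C = 1: 0.30/0.20 = 1.5, so 1.25 × 1.5 = 1.88

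A main-effects logistic model (R on period and C, fitted to expected counts) returns one odds ratio between these:

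| Care among ROSC patients, before to after | Multiplier C=0 / C=1 | Adjusted period OR (true 1.25) |
|---|---|---|
| 20% to 20% | 1 / 1 | 1.25 |
| 20% to 22% | 0.975 / 1.10 | 1.24 |
| 20% to 25% | 0.9375 / 1.25 | 1.21 |
| 20% to 30% | 0.875 / 1.5 | 1.17 |
| 20% to 40% | 0.75 / 2.0 | 1.08 |
| 30% to 20% | 1.143 / 0.667 | 1.33 |

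With ROSC before at 5% to 15%, the last three rows become 1.20–1.15, 1.12–1.04 and 1.31–1.35. With no true effect (9% in both periods), they become 0.94, 0.87 and 1.06, so an apparent effect can arise from nothing.

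**2. Bundle steps as covariates.** Suppose survival follows a logistic model in period and one binary step M, present in 40% before. The intercept is solved to give 9% before, and the period coefficient to give 11% after, when M rises by d. The total odds ratio is 1.25 throughout.

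| OR of M on survival | d | Period OR adjusted for M | Share of log OR left |
|---|---|---|---|
| 1.5 | 5 points | 1.23 | 91% |
| 2.0 | 10 points | 1.17 | 70% |
| 2.5 | 20 points (extreme corner) | 1.05 | 22% |

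For the primary outcome the plan gives no rate. With 3% to 7% assumed before and the same total odds ratio, the three results are 1.22–1.23, 1.17 and 1.05.

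**3. Non-collapsibility.** Models 2–4 would also contain strong prognostic factors. Add one such factor to the setup in step 2 (20% prevalence, odds ratio 10, independent of period) and solve again. The first case moves from 1.23 to 1.27, above the crude 1.25, and the second from 1.17 to 1.21. The effect through M is still left out, but the direction of the change from crude to adjusted is not assured.

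**The case against.** Several counter-arguments carry weight.

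- **The certain error is narrow.** It concerns the tertiary outcome in two of four models. Models 1 and 2 contain no post-resuscitation care, so ROSC estimates free of this error are already planned. For the two discharge outcomes, this care precedes the outcome. This stands.
- **The size may be small.** A shift in care from 20% to 22% moves the odds ratio only from 1.25 to 1.24. This stands too, but it does not justify the adjustment, which offers nothing in return.
- **The covariate list is inferred.** Variables and measurement says what was collected, not what enters each model. Model 4's ACLS group is not one of its four groups, and airway and fluid items listed there under EMS may have been moved into it. The second problem is therefore conditional. The shared group names make it the natural reading, but not a certain one.
- **An estimate free of bundle steps exists.** The absolute differences and Model 1 provide one. However, they omit location and witness status, and no listed model takes in those two without the rest of the community and EMS groups.
- **A historic control calls for adjustment for change over time.** This is a fair reason to keep Models 2–4. It does not make them estimates of the overall effect, because the same variables can carry both bundle effects and background change.

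A reader might infer that Models 2–4 must shrink the bundle's odds ratio. Step 3 of the working shows that this does not follow. A reader might also infer that the primary result is invalid or that the plan has no overall-effect estimate. The documents support neither.

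**Conclusion.** As written, adjusting prehospital ROSC for post-resuscitation care in Models 3 and 4 is an error. It rests only on the unrestricted wording of the Statistical analysis section and on the order of events. Its size cannot be found from the documents. Over the assumed shifts in care it ranges from negligible (1.24 against 1.25) to material (1.08 or 1.33), in either direction, and is nil if use of care given ROSC status did not change.

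The second point holds if the covariate groups contain the items listed under the same names. Models 2–4 then leave out the effect carried by bystander CPR and the detection and response intervals, and do not answer the stated purpose. Confidence here is moderate.

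The undefined ACLS group and the unlisted group contents are matters for clarification only. The text does not show whether Model 4 adjusts for the feedback-defibrillator or multi-tier programs themselves, so no such claim is made.

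**What to change.** 1. Remove post-resuscitation care from every prehospital-ROSC model, including Model 4.
2. Add one period model with demographics, location of arrest, witness status and the ambulance-station random intercept. Report it beside the absolute differences as the estimate of overall effect. Initial rhythm is left out because it is recorded at the scene, after dispatcher and bystander steps may have acted.
3. Keep Models 2–4, labelled as explanatory or sensitivity analyses that do not estimate the overall effect.
4. For clarity, list the items in each covariate group and define the ACLS group.

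The cost is some SAP wording and one extra model on variables already collected. The drawback is that, with a historic control, the added model credits to the bundle any unrelated change over time in bystander CPR, EMS practice (the protocols were revised on the 2010 and 2015 guidelines) and hospital care. Models 2–4 should therefore still be reported, though they separate the two only in part. The section is in the past tense and cites software accessed in February 2018. If the analyses have already been run, the change means a short reanalysis, and the added model should be labelled post hoc.
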